7.5. Randomisation Procedure / Code Break

This study will employ an open-label, within-subject design with repeated sessions. Each participant in stage 1 of the study will receive all five treatment conditions in a random sequence. A randomisation schedule will be created using five treatment conditions with a corresponding code as per Table 2.

Table 4 Treatment Coding for Randomisation

Treatment Code:	Drug administration and dosage	IMP/Comparator
Α	Buccal administration of 2mg naloxone rapid dispersal wafer	IMP
В	Buccal administration of 4mg naloxone (2x 2mg) rapid dispersal wafers	IMP
С	Sublingual administration of 2mg naloxone rapid dispersal wafer	IMP
D	IM administration of 0.4mg/1ml naloxone ampoule	Comparator
E	IN administration of 1.8m/0.1ml naloxone (Nyxoid®)	Comparator

Another randomisation schedule will be created accordingly for stage 2 of the study if the study does not terminate early (i.e., when at least one of the IMPs is selected for further evaluation)

7.5.1. Method of Assignment to Treatment Ordering

Each participant will be assigned a unique study number upon pre-screening (P001; P002, P003 etc), screening (e.g. S001, S002, S003 etc), and randomisation (R001, R002, R003 etc), allocated sequentially in the order of assignment.

The unique randomisation study number allocated to each participant will correspond with the randomisation schedule. The randomisation schedule will determine the order of treatment for each participant.

The randomisation schedule will be stored securely and will only be accessible to authorized personnel not directly involved in participant assessments.

7.5.2. Randomisation

At each experimental visit, the appropriate treatment will be administered according to the predetermined randomisation schedule.

If a participant withdraws from the study before completing all dosing visits, a new randomisation number will be assigned to any replacement participant, no randomisation number will be re-used.

Randomisation service will be provided by the King's Clinical Trial Unit (CTU).

Each randomised participant will be provided with a card detailing emergency contact details. Participants will be requested to carry this card with them at all times while participating in the trial.

7.5.3. Emergency Code Break

As this is an open-label study, there is no need for a code break procedure. The treatment allocation for each session will be known to both the investigators and participants.

7.6. Withdrawal of Participants

- i. Withdrawal of consent.
- ii. Significant abnormalities detected during the medical assessment or blood tests at the screening visit.
- iii. Suspected Unexpected Serious Adverse Reaction.
- iv. Participant does not attend follow-up point.
- v. Investigator discretion.

Session-specific exclusions:

If a participant meets any of the following session-specific exclusion criteria, the session will be postponed and rescheduled for a later date. The participant will remain enrolled in the study and can complete the remaining sessions as planned, provided they meet all criteria at the time of the rescheduled session.

- i. Use of any over-the-counter medications containing codeine or other opioids, prescribed opioid medication or of illicitly obtained opioids within the past 2 weeks (if the participant is taking a long-acting opioid the period might, after consideration by the examining doctor, be extended to 4 weeks or longer according to washout period).
- ii. Urine drug screen positive for any substance on the day of the session.
- iii. Positive alcohol breath test (above 0) on the day of the session.
- iv. Presence of any acute respiratory symptoms (such as cough, shortness of breath, sore throat), suspected/confirmed COVID-19, other respiratory infection or any other acute disease at the investigator's discretion.

Participants have the right to withdraw from the study at any time for any reason. The investigator also has the right to withdraw participants from the study drug in the event of intercurrent illness, AEs, SAEs, SUSARs, protocol violations, administrative reasons, or other reasons. It is understood by all concerned that an excessive rate of withdrawals can render the study un-interpretable; therefore, unnecessary withdrawal of participants should be avoided. Should a participant decide to withdraw from the study, all efforts will be made to report the reason for withdrawal as thoroughly as possible.

If participants are withdrawn prior to completing all five experimental visits and are therefore missing a full dataset from experimental visits, they will be replaced. Participants lost to follow-up will not be replaced.

In the event of early withdrawal, any data already obtained, such as pharmacokinetic and safety, can be retained by the study and may be used in analyses and presented in publications.

Withdrawal Due to Missed Visits:

Since this is a 5-way crossover requiring all treatments for analysis, missing 2 consecutive scheduled visits or 3 total visits should constitute withdrawal, as incomplete data would compromise the crossover design.

Lost to follow up:

For contact attempts before classifying participants as lost to follow-up we would make three contact attempts over a one-week period using multiple communication methods including phone calls, emails, and text messages if participants have consented to receive them. These

attempts should be spaced at 24 hours, three days, and seven days after a missed appointment, with each attempt using a different contact method when possible. All contact attempts should be thoroughly documented in the source documents, and participants should be classified as lost to follow-up only after all three attempts have failed to elicit any response.

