11.1. Sample Size

No formal sample size calculation is computed as this is a pharmacokinetic study. Treatment selection will be made based on complete data of 12 participants (with five responses from each participant, each for an arm) at stage 1. With an expected drop-out rate of 20%, we expect to randomise 15 participants. This sample size exceeds the EMA recommendations for minimum sample size in pharmacokinetic studies for comparing formulations, providing robust data for analysis.

Stage 2 will recruit 30-35 participants, depending on the dropout rate observed in stage 1. A cross-over design will be implemented in stage 2 where the number of arms depend on the findings from stage 1. Participants that partake in stage 1 will not be eligible to also participate in Stage 2.

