 Laboratory parameters including haematology, blood chemistry, and urinalysis will be listed accompanied by an indication if the parameter is outside the reference range. A summary of all data outside the reference range of the clinical laboratory will be provided. Clinical laboratory data will be presented descriptively, where applicable.

Adverse events:

A listing of all individual AEs, AR, UAR, SAE, SAR and SUSAR will be provided. Summary tables of the TEAEs will be presented by the system organ class based on the MedDRA terminology list (preferred terms): 1 containing the number of TEAEs (frequency of occurrence, number of participants experiencing the event) by treatment and 1 containing the number of drug related TEAEs (frequency of occurrence, number of participants experiencing the event) per treatment. Additional tables of total counts by treatment and relationship and by treatment and severity will be given.

Missing data handling:

• This study will employ a complete case analysis approach, where only data from participants with full observations for a given endpoint will be included in the primary analysis for that endpoint. However, in the event of early withdrawal, any data already obtained (such as pharmacokinetic and safety data from completed visits) will be retained by the study and may be used in secondary analyses and presented in

publications, where scientifically appropriate. For participants who withdraw after completing at least one but not all experimental visits, their data from completed visits may be included in per-visit analyses.

12. Trial Management Group (TMG)

The TMG will include the Chief Investigator, co-investigators, the statistician, and the trial manager. The TMG will be responsible for overseeing the trial. Since it's a small pharmacokinetic study which is expected to be completed within a few months, we will meet on an ad hoc basis as and when any issues with the trial arise.

The TMG will review recruitment figures, SAEs and substantial amendments to the protocol prior to submission to the REC and/or MHRA.

13. Trial Steering Committee

The Trial Steering Committee (TSC) will provide overall supervision of the trial, ensuring it is conducted according to the protocol and in compliance with Good Clinical Practice (GCP) requirements. The TSC will monitor progress of the trial and recommend any appropriate amendments/actions for the trial as necessary.

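### The withdrawal and replacement rules in section 7.6 allow a participant to be incomplete yet unreplaced, so they do not secure the 12 complete datasets of section 11.1

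*Protocol*

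**What the plan says.** Four parts of the protocol bear on this.

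- **Missed visits (7.6).** The paragraph opens with its reason, "Since this is a 5-way crossover requiring all treatments for analysis", and then sets the threshold: "missing 2 consecutive scheduled visits or 3 total visits should constitute withdrawal, as incomplete data would compromise the crossover design".
- **Replacement (7.6 and 7.5.2).** Participants who are withdrawn before finishing all five experimental visits, and so lack a full dataset, are replaced. Section 7.5.2 likewise ties a replacement to a withdrawal. The next sentence of 7.6 is "Participants lost to follow-up will not be replaced". The lost-to-follow-up paragraph starts that classification from a missed appointment, with contact attempts at 24 hours, three days and seven days. It does not limit it to the post-dosing call.
- **Sample size (11.1).** "Treatment selection will be made based on complete data of 12 participants", with five responses from each. "With an expected drop-out rate of 20%, we expect to randomise 15 participants". There is no power basis: "No formal sample size calculation is computed as this is a pharmacokinetic study".
- **Missing data (11.3).** For each endpoint, "only data from participants with full observations for a given endpoint will be included in the primary analysis for that endpoint".

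Section 7.6 postpones and reschedules a session for four listed session-specific reasons (opioid use, positive drug screen, positive breath test, acute illness). Non-attendance is not among them. Section 6.2.1 foresees dosing that runs past three months, after repeat screening.

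**The concern.** The missed-visit rule does not follow from its own reason. If every treatment is needed for analysis, one missed treatment already makes a participant incomplete, but the rule acts only at two in a row or three in total. Because replacement depends on withdrawal, a participant below that threshold has no stated route to replacement.

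For someone who disappears during dosing, the label rather than the data can decide whether a replacement is made. Suppose visits are two days apart, which the 36-hour washout permits. Two consecutive misses then occur before the seven-day contact attempt, so the participant is withdrawn and replaced. If visits are more than a week apart, all three contact attempts can fail before a second visit is missed. The participant is then lost to follow-up and not replaced. The data may be equally incomplete in both cases.

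Under section 5.4, stage 1 decides whether each wafer arm continues and whether the study goes on at all. The stated basis is only 12 people, so losing two or three of them matters.

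**Working it through.** **The plan's own figure.** Inputs from 11.1: 12 complete participants and 20% drop-out. 12 / (1 − 0.20) = 15. The 15 is reproduced.

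**Attendance patterns that escape the missed-visit rule.** Five visits, each attended or missed, give 2^5 − 1 = 31 incomplete patterns. Of the 10 two-miss patterns, 4 are adjacent and 6 are not.

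| Visits missed | Patterns | Withdrawn by rule | Not withdrawn by rule |
|---|---|---|---|
| 1 | 5 | 0 | 5 |
| 2 | 10 | 4 | 6 |
| 3 | 10 | 10 | 0 |
| 4 | 5 | 5 | 0 |
| 5 | 1 | 1 | 0 |
| Total | 31 | 20 | 11 |

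11/31 = 35% of patterns.

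**Share of incomplete participants.** This needs an assumption, because the protocol gives no missed-visit rate. Two contrasting models:

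- *Sporadic misses*, independent with probability q per visit and not made up. The share in the gap is [5q(1−q)^4 + 6q²(1−q)³] / [1 − (1−q)^5]. At q = 0.044 (20% incomplete) it is 0.193/0.200 = 96%. At q = 0.10 it is 0.372/0.410 = 91%, and at q = 0.20 it is 0.532/0.672 = 79%. It falls below half only above about q = 0.40.
- *Stopping for good.* There are five such patterns, and 4 of them meet the missed-visit rule. The exception is a participant who misses only visit 5. Any formal withdrawal is replaced in any case.

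**Does 15 randomised secure 12?** In the worst case nobody incomplete is replaced, and the number complete is binomial with n = 15.

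| Incomplete | Expected complete | P(at least 12 complete) |
|---|---|---|
| 10% | 13.5 | 0.944 |
| 15% | 12.75 | 0.823 |
| 20% (the plan's rate) | 12.0 | 0.648 |
| 25% | 11.25 | 0.461 |
| 30% | 10.5 | 0.297 |

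At 20% the terms for 12, 13, 14 and 15 complete are 0.250 + 0.231 + 0.132 + 0.035 = 0.648.

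If participants who trigger the missed-visit rule are replaced and only those in the gap are not, the sporadic model at 20% gives a complete share of 0.800 / (0.800 + 0.193) = 0.806. The chance of at least 12 is then 0.671. If incompleteness is instead mainly formal withdrawal, the replacement rule covers nearly all of it and the shortfall is small.

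**The case against.** The strongest case against has five parts.

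1. *A missed appointment need not be a missed treatment.* Sessions can be postponed, dosing can run late after repeat screening, and the missed-visit rule can be read as a limit on repeated non-attendance by people who are otherwise rebooked. This stands in part. It is why the point is confined to visits that are not made up. But the rescheduling rule lists four reasons and non-attendance is not one of them, so the text leaves the question open.
2. *The investigator may withdraw anyone for administrative or other reasons, which makes them replaceable.* True, and it reduces the shortfall. It is discretion rather than a rule, and 7.6 also asks that unnecessary withdrawals be avoided. The 7.6 list of withdrawal reasons includes not attending a follow-up point. Reading that as any dosing visit would leave the missed-visit threshold without purpose.
3. *Fifteen is an expectation, not a cap, and selection is stated to use 12.* True. But the only stated way to add a participant for an incomplete one is replacement, and that is tied to withdrawal.
4. *Lost to follow-up plainly means the call 7 to 14 days after the last dose.* This is a natural reading, but the protocol starts the classification from any missed appointment.
5. *Data are not thrown away.* This stands. The complete-case rule applies to the primary analysis of each endpoint, and 11.3 keeps completed-visit data for secondary and per-visit analyses.

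A reader might infer that most incomplete participants go unreplaced, or that all of them are dropped from the trial's analyses. The documents support neither. The first depends on an assumed pattern of sporadic misses: by pattern count the figure is 35%, and drop-out in the usual sense is largely replaced. The second ignores the per-endpoint rule.

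**Conclusion.** The point holds as an inconsistency between stated rules. Section 7.6 says all five treatments are needed, but it leaves 11 of 31 incomplete patterns with neither withdrawal nor replacement by rule. It also lets a participant who disappears during dosing fall under two rules with opposite consequences. The 12 complete datasets in 11.1 are therefore met on average, not secured. At the plan's own 20%, the chance that 15 randomised yield at least 12 is 0.648 if none are replaced.

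That figure is a worst case. It assumes that the 20% means lacking a full set of treatments, that participants are independent, and that neither rebooking nor discretionary withdrawal fills the gap. The true shortfall could be much smaller: at 2% missed per visit, the expected number complete is 15 × 0.98^5 = 13.6, above 12. At 5% it is 15 × 0.95^5 = 11.6, but that rate implies about 23% incomplete, more than planned. The protocol gives no basis for choosing between these rates. The text should be corrected because the rules as written can leave selection short of its stated basis and the remedy is cheap.

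**What to change.** In 7.6, define replacement by data rather than by label. Suggested wording: *Any participant who ends dosing without an evaluable PK profile for every scheduled treatment of the stage is replaced, until the stated number of complete datasets is reached. Participants who miss only the post-dosing follow-up contact are not replaced.*

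Reconcile the missed-visit and lost-to-follow-up paragraphs, and the replacement sentence in 7.5.2, with this wording. State whether a visit missed through non-attendance may be rescheduled. Referring to the treatments of the stage also makes the rule usable in stage 2, where the number of visits is not yet fixed.

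The cost is a protocol wording change and possibly a few more participants than 15. With replacement until 12 are complete, the expected number randomised at 20% incomplete is still 12 / 0.8 = 15, though the actual number could be higher.

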7.7. Expected Duration of Trial

The end of the trial will be defined as database lock.

8. Trial Procedures

The overall trial design for each participant, from screening to final follow-up is detailed in 5.5 Trial Flowchart. The study schedule of assessments (section 8.1) details timing of procedures planned for experimental visits 1-5, pre-dose and post-dose.

As per 6.2 Dosing Regime, there will be a minimum of 36 hours between each of the five experimental visits.

A breakdown of all study assessments is detailed by visit in section 8.2.

8.1. Study Schedule of Assessments

Table 5 Assessment Timepoints for each of the Experimental Visits in Stage 1

Assessment	Timepoint																
	Pre-c	dose	Post-dose														
	Pre	-5m	0m	2m	4m	6m	8m	10m	12.5m	15m	30m	45m	1h	1.5h	2h	4h	> 4h
Eligibility assessment/review	Х																
Urine pregnancy	Х																
Urine drug screen	Χ																
Alcohol breath test	Χ																
IV cannulation	Х																
Vital sign assessments ¹	Х							Х			Х		Х			Х	
Treatment allocation/ randomisation ²	Х																
IMP administration ³			Х														
Administration site check ⁴	Х										Х					Х	
PK blood sampling		Х		Х	Х	Х	Х	Х	Х	Х	Х	Х	Х	Х	Х	Х	
Wafer disintegration time ⁵			Х														
Visual Analogue Scale (VAS) ⁶			Х														
Discharge																	X ⁷
AE Review ⁸		Х						Х			Х		Х			Х	
Conmed review	•		•	•							•			•		1	

In this five-way crossover design study in stage 1, all treatment experimental visits will follow this schedule.

- 1. Vital sign assessments include. Heart rate, respiratory rate, blood pressure, and oral body temperature.
- 2. Each participant will be assigned a randomised treatment allocation sequence for drug administration ordering either at or before visit 1, pre-dose.
- 3. IMP administration is allocated according to the randomised treatment allocation ordering, determined at visit 1, pre-dose.
- 4. For buccal and sublingual treatment arms, oral mucosa will be examined with any changes documented. IM injection site and nasal cavities will be examined in the other arms.
- 5. Wafer disintegration time only recorded for buccal and sublingual naloxone administration visits.
- 6. VAS assessment completed by participants immediately following administration of each oral formulation to assess taste and tolerability.
- 7. Discharge at least 4 hours post dose at minimum.
- 8. AE review reported at anytime, however participants will be prompted by research staff at these timepoints.

8.2. By Visit

All in-house visits will be performed and held at the CRF. Trial procedures will be performed by a trained member of the research team or CRF staff.

8.2.1. Screening Visit

The screening visit will be performed at a maximum of 28 days prior to IMP administration/Visit 1. At the end of the visit, each participant will be provided with a card detailing emergency contact details.

The following interventions and assessments will be completed in order:

- i. Informed consent
- ii. Collection of demographic information
- iii. Medical review and physical examination (including review and documentation of current medications).
- iv. Height, weight, BMI
- v. Review of eligibility
- vi. Urine sample for urinalysis, pregnancy, and illicit drug testing (see section 8.3 for full list)
- vii. Alcohol breath test
- viii. Blood tests: LFTs; FBC & U&Es (see section 8.3 for full list)
- ix. Vital Signs
- x. ECG

8.2.2. Visits 1-5: Experimental visits for Stage 1

- 1. Randomisation to the treatment schedule ordering at or before Visit 1 as per Section 7.5 and Section 11.3.
- 2. Administration of IMP:

As this is an open-label study, participants will be informed of the dosing schedule. There will be a minimum 36 hrs washout between experimental visits.

For all five visits, the administration site will be checked pre-dose, and 30min & 4h post.

For buccal and sublingual IMP formulations, wafer disintegration time will be measured.

3. VAS:

Participants will complete a 100mm VAS immediately after administration of each formulation to assess taste and local tolerability.

4. Blood sampling:

Given the special interest in early absorption, blood collection included intense sampling during the first 15 minutes, with a total of 14 samples per session (pre-dose, at 2, 4, 6, 8, 10, 12.5, 15, 30 and 45 minutes and 1, 1.5, 2, 4 hours post-dose).

5. Vital signs:

Vital signs (HR, RR, BP, Temp) will be recorded on experimental visits at the following times: pre-dose, 10 minutes, 30 minutes, 1 hour, and 4 hours.

6. Adverse events and conmed checks:

Participants will be asked to report adverse events at specific timepoints (pre-dose, 10 minutes, 30 minutes, 1 hour, and 4 hours) during each experimental visit. Additionally, participants will be instructed that they can report any adverse events to the research

team at any time throughout their participation in the study. Conmed checks will be checked along with AEs.

The following interventions and assessments will be completed in order:

- i. Eligibility review
- ii. Review of any new medications or changes in medication since last visit
- iii. Urine sample for pregnancy and illicit drug testing
- iv. Alcohol breath test
- v. IV cannulation
- vi. Treatment allocation
- vii. Pre-dose; 0-5mins: blood sampling; vital signs; adverse events assessment; administration site check
- viii. 0 mins: drug administration; wafer disintegration time (for buccal and sublingual visits only): visual analogue scale
- ix. 2 mins: blood sampling
- x. 4 mins: blood sampling
- xi. 6 mins: blood sampling
- xii. 8 mins: blood sampling
- xiii. 10 mins: blood sampling; vital signs; adverse events assessment
- xiv. 12.5 mins: blood sampling
- xv. 15 mins: blood sampling
- xvi. 30 mins: blood sampling; vital signs; adverse events assessment; administration site check
- xvii. 45 mins: blood sampling
- xviii. 1 hour: blood sampling; vital signs; adverse events assessment
- xix. 1.5 hrs: blood sampling
- xx. 2 hrs: blood sampling
- xxi. 4 hrs: blood sampling; vital signs; adverse events assessment; administration site check
- xxii. > 4 hrs: discharge

8.2.3. Washout:

There will be a minimum 36 hrs washout between experimental visits.

